### 11.3 Clinical laboratory evaluations

Laboratory data (clinical chemistry, hematology, and urinalysis) and changes from Baseline (if applicable) for numeric variables will be listed by PS0016 randomized treatment group and visit. Any laboratory variables with values that are BLQ or ALQ will be handled as described in [Section 4.2.2](#) for calculation of changes from Baseline and for summary tables. Values outside the reference range for the numeric variables will be flagged in the listings.

Clinical chemistry and hematology variables will be summarized by PS0016 randomized treatment group at each visit, for both absolute values and changes from PS0016 Baseline.

Laboratory variables will be grouped according to the laboratory function panel and categorized as normal, high or low, if applicable, based on the reference range supplied by the analytical laboratory. For selected variables that are identified in [Table 11-1](#), the change in category from Baseline will be presented in shift tables at all PS0018 visits.

The number and percentage of subjects with treatment-emergent markedly abnormal (TEMA) laboratory results will be tabulated by PS0016 randomized treatment group and visit. Markedly abnormal laboratory values will be defined as those categorized as Grade 3 and above based on the ranges defined as per the Common Terminology Criteria for Adverse Events (CTCAE) Version 4.03 (2016). These are provided in [Table 14-2](#). The tabulation will include a category for the incidence of TEMA results over all visits which will also count unscheduled measurements.

Laboratory measurements meeting the criteria for TEMA will be listed separately for hematology and chemistry. The listings will include all measurements for any variable with at least one TEMA result for each subject.

Any additional laboratory variables not included in the outputs described previously will be listed separately. These will include the following:

- Pregnancy tests (serum and urine)
- Follicle stimulating hormone (FSH) (only for postmenopausal women)

Subjects with treatment-emergent liver function test abnormalities at any PS0018 visit will be summarized (number and percentage of subjects) by PS0016 randomized treatment group. The criteria for this tabulation are presented in [Table 14-3](#).

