#### **3.2 Secondary objectives**

Secondary objectives of the study are:

- To assess the safety and tolerability of increasing the dose of bimekizumab from 160mg Q4W to 320mg Q4W for subjects with an inadequate response at Week 12
- To assess PK of bimekizumab
- To assess the immunogenicity of bimekizumab
- To assess the efficacy of open-label bimekizumab 160mg Q4W administered over 48 weeks

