#### 2.1.2 Secondary objectives

Secondary objectives of the study are:

- To assess the safety and tolerability of increasing the dose of bimekizumab from 160mg every four weeks (Q4W) to 320mg Q4W for subjects with an inadequate response at Week 12
- To assess pharmacokinetics (PK) of bimekizumab
- To assess the immunogenicity of bimekizumab
- To assess the efficacy of open label bimekizumab 160mg Q4W administered over 48 weeks

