**Table 3–1: Treatment group assignment for the TFLs**

TFL group	PS0016 randomized treatment group			PS0018 dose at onset			Dose adjustment group	
	BKZ 320mg + PBO	BKZ 320mg	All Subjects	BKZ 160mg Q4W	BKZ 320mg Q4W	All BKZ	Non- adjuster	Adjuster
Subject disposition	X	X	X					
Protocol deviations	X	X	X					
Demographics	X	X	X					
Medical history	X	X	X					
Prior/concomitant medications	X	X	X					
Compliance	X	X	X					
Exposure				X	X	X		
AEs a	X	X	X	X	X	X	X	X
Safety data (including vital signs, ECGs and laboratory tests)	X	X						
Efficacy (except PASI)	X	X	X					
PASI	X	X	X				X	X
Pharmacokinetic data	X	X						
ADA	X	X						

ADA= anti-bimekizumab drug antibody; AE=adverse events; ECG= electrocardiogram; IMP= investigational medicinal product; Q4W= every four weeks; TFL= tables, figures, and listings.

aSelect tables presenting TEAEs by PS0016 randomized treatment group and Dose adjustment group, as defined in [Section 11.2.3](#).

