## 11.4 Vital signs, physical findings, and other observations related to safety

### 11.4.1 Vital signs

Vital signs will be measured at every visit and will include:

- Systolic and diastolic blood pressure
- Pulse rate
- Body temperature (oral, axillary, or otic)

Vital signs are to be measured prior to blood sampling, and prior to dosing, where applicable.

A by-subject listing of all vital sign measurements and changes from Baseline will be presented by PS0016 randomized treatment group and visit. The listing will include a flag for measurements identified as TEMA/potentially clinically significant (PCS) as calculated by the criteria outlined in [Table 14-4](#).

Descriptive statistics will be reported for all vital sign measurements. Measured values and changes from Baseline will be summarized by vital signs variable and visit for each PS0016 randomized treatment group.

The number and percentage of subjects with TEMA/PCS vital sign values will be summarized by PS0016 randomized treatment group and variable at each visit and overall (ie across all PS0018 visits).

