#### **11.4.3 12-Lead Electrocardiograms**

Standard 12-lead ECG will be recorded after 10 minutes of rest in the supine or semi recumbent position. The following ECG variables will be recorded together with the Investigator's interpretation of the ECG profile:

- Heart rate
- PR interval
- QRS duration
- QT interval
- QT corrected for heart rate using Fridericia's formula (QTcF)

The results of all ECG variables will be reported in the by-subject listings. The listing will also include the change from Baseline for numeric parameters and will be presented by PS0016 randomized treatment group and visit.

Measured values and changes from Baseline will be summarized for each variable by PS0016 randomized treatment group and visit.

The following cut-points in QTcF (raw data and change from Baseline) will be summarized categorically by PS0016 randomized treatment group (number and percentage of subjects) and visit. The denominator for the percentages will be the number of subjects with a non-missing measurement for the variable at the specific visit.

Raw QTcF data:

- <450msec
- ≥450 msec to <480msec
- ≥480msec to <500msec
- ≥500msec

Change from Baseline QTcF:

- <30msec
- $\geq 30$ msec to <60msec
- $\geq 60$ msec

Electrocardiogram findings will be listed separately.

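### Threshold tables for laboratory, liver, vital-sign and QTcF results are grouped only by PS0016 arm, so in the summary tables the dose-increase safety objective is addressed through adverse events alone

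*SAP*

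**What the plan says.** The first secondary objective in Protocol 3.2, repeated in SAP 2.1.2, is "To assess the safety and tolerability of increasing the dose of bimekizumab from 160mg every four weeks (Q4W) to 320mg Q4W", in subjects whose Week 12 response is inadequate. Both documents name laboratory values, vital signs and ECG as safety variables.

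The SAP groups the tables of abnormal values as follows:

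- TEMA laboratory results (SAP 11.3): "The number and percentage of subjects with treatment-emergent markedly abnormal (TEMA) laboratory results will be tabulated by PS0016 randomized treatment group and visit".
- Liver abnormalities (SAP 11.3, criteria in 14.2): "Subjects with treatment-emergent liver function test abnormalities at any PS0018 visit will be summarized (number and percentage of subjects) by PS0016 randomized treatment group". SAP 14.3.8 sends Hy's Law cases to this table too.
- Vital signs (SAP 11.4.1): "The number and percentage of subjects with TEMA/PCS vital sign values will be summarized by PS0016 randomized treatment group and variable at each visit", and across all visits.
- QTcF cut-points (SAP 11.4.3): "will be summarized categorically by PS0016 randomized treatment group (number and percentage of subjects) and visit".

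SAP Table 3–1 (treatment group assignment for the TFLs) agrees. Its row "Safety data (including vital signs, ECGs and laboratory tests" is marked only under the two PS0016 arms. It has no mark under All Subjects, PS0018 dose or dose-adjustment group.

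Adverse events are treated differently. SAP 11.2.3 tabulates TEAEs and events of special monitoring by PS0018 dose at onset, with selected tables by adjuster group. Exposure is also shown by PS0018 dose.

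**The concern.** The PS0016 arm does not tell the reader what a subject was taking when a PS0018 value was measured. Both PS0016 arms received 320mg at Baseline and Week 4 and differed only at Week 16 (placebo against one further dose). In PS0018 everyone starts on 160mg, and some may go to 320mg from Week 12. Each PS0016 column therefore mixes values from both PS0018 doses. A cluster of abnormal blood pressures or QTcF values arising on 320mg would be spread over two columns that are not defined by dose. One of those columns is labelled BKZ 320mg, which invites confusion with the PS0018 dose.

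At stake is whether the study report can show, for the measured safety variables, what happened after the dose increase that the objective names.

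**Working it through.** No sample-size or error-rate figure in the plan bears on this point, so the check is a cross-reading, a visit count and two illustrations.

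**1. Grouping.** Of the four threshold outputs (TEMA laboratory, liver, TEMA/PCS vital signs, QTcF categories), the number with a PS0018-dose or adjuster column is 0 of 4. SAP 3.6 makes actual PS0018 treatment the default for the Safety Set, but only where Table 3–1 does not say otherwise. Here it does, so the default does not apply.

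**2. Where doses can mix.** From Protocol Table 5–1, with visit assessments made before dosing and the first increase possible at Week 12, the first values after an increase fall at Week 16.

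| Data | Post-entry visits | Visits after Week 12 |
|---|---|---|
| Laboratory | 8, 16, 24, 32, 40, 48, SFU = 7 | 6 of 7 |
| ECG | 24, 48, SFU = 3 | 3 of 3 |
| Vital signs | every 4 weeks from 4 to 48, and SFU = 13 | 10 of 13 |

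The SFU values come 20 weeks after the last dose, so they reflect current dose least.

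**3. What the PS0016 columns would print.** Assumption: all 45 planned subjects roll over in the 2:1 ratio, giving 45 × 2/3 = 30 and 45 × 1/3 = 15. Suppose two subjects have an abnormal value, both on 320mg:

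- both in the larger arm: 2/30 = 6.7% and 0/15 = 0%
- one in each arm: 1/30 = 3.3% and 1/15 = 6.7%
- both in the smaller arm: 0/30 = 0% and 2/15 = 13.3%

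The same two cases give three different pictures, and none points to dose.

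**4. What a 320mg column could show.** The documents do not say how many subjects will reach 320mg, so m = 5, 10 and 15 are assumed. With no affected subject, the exact upper 95% limit is 1 − 0.025^(1/m). With two affected, the interval is Clopper–Pearson. The chance of seeing at least one case at a true risk of 10% (assumed) is 1 − 0.9^m.

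| m | 0 affected: upper limit | 2 affected: estimate (95% CI) | Chance of at least 1 case |
|---|---|---|---|
| 5 | 52.2% | 40.0% (5.3–85.3%) | 0.41 |
| 10 | 30.8% | 20.0% (2.5–55.6%) | 0.65 |
| 15 | 21.8% | 13.3% (1.7–40.5%) | 0.79 |

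The column would be imprecise, but it would place the cases on the dose where they arose.

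**5. The overall column.** Protocol 14.2.2 plans change from Baseline in laboratory values, ECG and vital signs by PS0016 group and overall. Table 3–1 does not mark All Subjects for these data. SAP 3.9 records three changes to the protocol analyses (physical examination, imputation method, pooled adjuster groups), and this is not one of them.

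**The case against.** A reader might infer that the plan gives no dose information on these variables, or that the objective cannot be answered. The documents do not support that, for four reasons.

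- SAP 3.1 flags 320mg time points in the listings. SAP 11.3 adds a separate listing of TEMA laboratory results, and the vital-sign listing flags TEMA/PCS values. With at most 45 subjects, case review by dose is feasible.
- Protocol 9.7.1 requires every PDILI event to be reported as an AE, so these enter the dose-at-onset tables. Cytopenias and hepatic events have their own tables by dose at onset.
- TEMA laboratory values are Grade 3 or above. Protocol 6.3 (criterion 10) withdraws such subjects, and under Protocol 6.4 more than one subject meeting the listed criteria brings in the DMC. Two such laboratory cases would not go unnoticed.
- The PS0016 grouping is prespecified in Protocol 14.2.2 with a reason, and SAP 3.6 expressly yields to Table 3–1. The grouping is therefore neither an internal contradiction nor a departure from the protocol.

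All of this stands, but it does not close the gap. The protocol's reason concerns change over time from the first randomization, not threshold abnormalities after a dose increase. AE coding does not reach every liver row: the bilirubin-only and ALP-only criteria in SAP Table 14–3 are not PDILI criteria. No special-monitoring category covers blood pressure or QTcF thresholds, and SAP 11.4.3 specifies no threshold flag in the ECG listing.

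It is also fair that a contrast of 160mg with 320mg would be confounded. The increase is open only to subjects with a PASI reduction of at least 50% but below 75%, at Week 12 or later. With a half-life of about 28 days (Protocol 2.2.1), carry-over blurs attribution after a return to 160mg.

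**Conclusion.** The point holds for the summary tables. None of the four threshold tables shows PS0018 dose, so in tabular form the dose-increase objective is addressed only through adverse events. The listings and AE-coded liver and cytopenia events supply part of what is missing; vital signs and QTcF are the least covered. The unrecorded loss of the overall column is a smaller, separate discrepancy with Protocol 14.2.2.

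The finding rests on SAP Table 3–1 and the section texts, not on a calculation. The percentages are illustrations that assume full rollover at 2:1 and an unknown number of subjects on 320mg. By-dose tables would help the report answer its own objective descriptively. They could not establish a dose effect, and their absence does not make the objective unanswerable.

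**What to change.** In SAP Table 3–1, 11.3, 11.4.1, 11.4.3 and 14.2:

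- Repeat the TEMA laboratory, liver, TEMA/PCS vital-sign and QTcF category tables with columns BKZ 160mg Q4W, BKZ 320mg Q4W and All BKZ.
- Assign each value to the last dose actually received before the measurement. A pre-dose value at the visit of the increase counts as 160mg. This needs its own derivation, because the listing flag starts at the time of the increase and can capture that pre-dose value.
- Use as denominator the subjects with at least one value on that dose, and show the numbers of subjects and measurements per dose. This matters most for ECG: a subject who increases at Week 12 and stays on 320mg has no post-entry ECG on 160mg.
- Keep the PS0016-arm tables for change over time, and either restore their All Subjects column or record its removal in SAP 3.9.
- State the limits beside the tables: small 320mg numbers, unequal measurement time per dose, carry-over after return to 160mg and at SFU, and a non-randomized contrast confounded by response and calendar time. Label the tables descriptive only.

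The cost is SAP wording, one derived variable and four repeated tables. No new data are needed.

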- 160mg loading dose followed by 80mg at Weeks 3 and 6
- 240mg loading dose followed by 160 mg at Weeks 3 and 6
- 560mg loading dose followed by 320mg at Weeks 3 and 6

The results of this study demonstrated that all doses of bimekizumab were well tolerated and there were no unexpected clinically relevant safety findings.

Infections (mostly nasopharyngitis) were the most commonly reported events in both the active treatment and the placebo group. None of the infections were considered serious or required treatment with antibiotics. Two subjects in the active treatment group experienced 1 local candida infection each (oropharyngitis and vulvovaginitis, respectively) that were nonserious and resolved with topical therapy. There was a reduction in mean neutrophil count in the active treatment group, although this drop was not clinically relevant and a clear relationship with dose or time was not evident. Some increases in liver function tests were reported, but none had a convincing relationship to exposure to study medication. The exploratory analysis showed clinically relevant improvement in activity of psoriatic arthritis and in skin involvement in those subjects with concomitant active psoriatic lesions.

Two additional studies of bimekizumab are ongoing. RA0123 is a Phase 2a, double-blind, randomized, placebo-controlled, multiple dose study to evaluate the safety, PK, pharmacodynamics, and efficacy of multiple doses of bimekizumab administered as add-on therapy to stable certolizumab pegol therapy in subjects with moderate to severe rheumatoid arthritis. UP0031 is a Phase 1 open-label, parallel-group, single-dose study to evaluate the relative bioavailability and tolerability of bimekizumab 160mg sc in healthy subjects.

Additional information on the clinical data for bimekizumab is available in the current version of the Investigator's Brochure (IB).

The current study, PS0018, is a 48-week open-label extension study for eligible subjects who participated in PS0016 (including subjects who relapse at Week 16 through 28 in PS0016), a Phase 2a, randomized, subject-blind, Investigator-blind study in adult subjects with moderate to severe chronic plaque psoriasis. In PS0016, subjects will be randomized 2:1 to receive the following study treatment regimens:

- Treatment arm A: Bimekizumab 320mg administered sc at Baseline and Week 4, followed by placebo administration at Week 16

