    - Persistent is defined as lasting 28 days or more, which spans at least 2 scheduled injections.

10. Subject has a clinical laboratory value meeting the following criteria:

- CTCAE Grade 3 and above: subjects must be withdrawn regardless of relationship to study drug or duration of event.
- CTCAE Grade 2
  - Subjects may remain in the study if the event is transient. If a subject has a Grade 2 laboratory abnormality, a retest is required within 1 to 2 weeks at a scheduled or unscheduled visit. If the repeat value is below Grade 2, the subject may receive the next scheduled study treatment. If the value on the repeat is still Grade 2 or above, a second repeat test must be performed and results made available prior to the next scheduled study treatment. If this second repeat value is still Grade 2 or above, the subject must be withdrawn.

11. Subject has active suicidal ideation as indicated by a positive response (“Yes”) to questions 4 or 5 or to the suicidal behavior questions of the “Since Last Visit” version of the self-rated Columbia-Suicide Severity Rating Scale (C-SSRS). The subject should be referred immediately to a Mental Healthcare Professional and must be withdrawn from the study.

12. Subjects with a HADS-D score  $\geq 15$  must be withdrawn. Any subject who develops a HADS-D score of  $>10$  during the study should be referred immediately to a Mental Healthcare Professional for further evaluation and potential withdrawal by the Investigator.

13. Subject does not achieve a PASI50 at Week 12 or later following open-label treatment in PS0018.

14. Subjects with newly diagnosed Inflammatory Bowel Disease (IBD) or with IBD flares during the study must:

- Be referred, as appropriate, to a healthcare professional treating IBD, such as a gastroenterologist
- Discontinue the IMP and be followed-up until resolution of active IBD symptoms

If IBD flares increase in severity or frequency during the study, the Investigator should use clinical judgment in deciding whether the subject should continue in the study and contact the Medical Monitor and UCB study physician to confirm the subject's suitability for continued participation in the study.

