## 6.4 Study stopping rules

During the study, planned dosing and procedures may be discontinued or suspended for all subjects in any part of the study and appropriate follow up procedures established. Where it is possible to do so without threatening the safety of subjects, such discontinuation/suspension should be discussed with the UCB Study Physician prior to its implementation.

Possible reasons for discontinuation or suspension of the study include (but are not limited to):

- A pattern of AEs occurs that contraindicates the further dosing of enrolled / additional subjects, including (but not limited to):
  - More than 1 subject meets any individual Withdrawal Criteria 6, 9, 10, 11 or 12 (as provided in Section 6.3), regardless of whether they met the same or different criteria.
  - Once a second subject meets any of those criteria, referral to the DMC may not be delayed while awaiting the outcome of either case.

If the above criteria are reached, the DMC will meet as soon as possible to determine whether discontinuation or suspension of the study should occur, and to determine what investigations, analyses, procedural amendments, or other actions should occur, before making any recommendation regarding the possibility of recommencing the study. Further details on the role of the DMC are provided in [Section 9.8.7](#).

- If the Sponsor or its designees judges it necessary for medical, safety, regulatory, or any other reasons consistent with applicable laws, regulations, and GCP.

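### The graded laboratory table starts at CTCAE Grade 3, so it does not count subjects whom the protocol withdraws for a Grade 2 value confirmed on two repeats

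*SAP*

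**What the plan says.** SAP section 11.3 defines the TEMA category: "Markedly abnormal laboratory values will be defined as those categorized as Grade 3 and above". Table 14-2 lists the cut-offs. The only row for absolute neutrophil count (ANC) is below 1.0 x 10^9/L. The TEMA table is by visit, with an all-visits category that also counts unscheduled measurements. The TEMA listing is confined to variables with at least one TEMA result in that subject.

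Protocol section 6.3, criterion 10, has two arms. The first matches the TEMA cut: "CTCAE Grade 3 and above: subjects must be withdrawn regardless of relationship to study drug or duration of event". The second concerns Grade 2. It begins "Subjects may remain in the study if the event is transient", asks for a retest within 1 to 2 weeks and, if needed, a second one before the next dose, and ends: "If this second repeat value is still Grade 2 or above, the subject must be withdrawn".

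Protocol section 6.4 makes criterion 10 part of the study stopping rule. The DMC must meet if "More than 1 subject meets any individual Withdrawal Criteria 6, 9, 10, 11 or 12", whether the subjects met the same criterion or different ones.

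**The concern.** The reporting threshold lies above one of the two laboratory thresholds at which a subject must leave the study. The one laboratory table built on CTCAE grades could therefore be empty while subjects were being withdrawn, and the DMC convened, for laboratory values. A reader who goes to that table to learn whether laboratory changes ended treatment would not find the answer there.

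The SAP already handles this differently for the liver. Table 14-3 counts AST and ALT from 3 x ULN, below the cut of more than 5.0 x ULN in Table 14-2, and its rows correspond to liver values on which the protocol acts in section 6.3.1. Blood counts, electrolytes and creatinine have no equivalent, although cytopenias are a named topic for special monitoring in protocol section 9.6.

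**Working it through.** The plan gives no figure on this point to reproduce; the 45 subjects are carried over from the feeder study (protocol section 14.7). The check compares the rules and then illustrates the result.

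**Step 1: follow one case.** Safety laboratory tests are scheduled at Baseline, Weeks 8, 16, 24, 32, 40 and 48, and the safety follow-up (SFU) visit (protocol Table 5-1). Dosing is every 4 weeks. Suppose the Week 8 ANC is Grade 2. The first retest is due in Week 9 to 10 (8 + 1 to 8 + 2), and the second result must be available before the Week 12 dose. Neither retest coincides with a scheduled laboratory visit. If all three values are Grade 2, criterion 10 requires withdrawal. As none is below 1.0 x 10^9/L, the subject contributes 0 to TEMA at every visit and 0 to the all-visits category, and is not in the TEMA listing for ANC.

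**Step 2: see where else the case could appear.**

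- By-visit summaries (SAP 3.1, 11.3): the scheduled Week 8 value enters and can move the minimum. The two repeats do not, because SAP 4.3 keeps repeated and unscheduled post-dose values out. Persistence, which is what forces withdrawal, is not visible.
- Early withdrawal visit: its laboratory value may be mapped to a scheduled visit (SAP 4.4), again as one value without a grade.
- Shift tables: low, normal and high only, for selected variables.
- Laboratory listings: all values, with out-of-range flags, but no grade and no count.
- Disposition (SAP 5.1): a primary reason for discontinuation, but the documents do not show that the criterion number is recorded.
- AE discontinuation and cytopenia tables (SAP 5.1, 11.2.3, 14.3.4): only if the value is recorded as an AE.

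**Step 3: illustrate the size.** Assumptions: all 45 subjects are treated, k of them are withdrawn for persistent Grade 2 ANC, and none of the k falls below 1.0 x 10^9/L. Exact (Clopper-Pearson) limits are the 0.025 quantile of Beta(k, 45 - k + 1) and the 0.975 quantile of Beta(k + 1, 45 - k).

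| k (assumed) | Planned TEMA row | Row for confirmed Grade 2 or above | Exact 95% CI |
|---|---|---|---|
| 1 | 0/45 | 1/45 = 2.2% | 0.1% to 11.8% |
| 2 | 0/45 | 2/45 = 4.4% | 0.5% to 15.1% |
| 3 | 0/45 | 3/45 = 6.7% | 1.4% to 18.3% |
| 5 | 0/45 | 5/45 = 11.1% | 3.7% to 24.1% |

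For 0/45 the upper limit is 1 - 0.025^(1/45) = 7.9%. That bound concerns Grade 3 and above; it says nothing about Grade 2.

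**Step 4: ask how likely such cases are.** With an assumed risk p per subject, P(at least 1) = 1 - (1 - p)^45 and P(at least 2) = 1 - (1 - p)^45 - 45p(1 - p)^44.

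| p (assumed) | At least 1 | At least 2 |
|---|---|---|
| 1% | 36.4% | 7.5% |
| 2% | 59.7% | 22.7% |
| 5% | 90.1% | 66.5% |
| 10% | 99.1% | 94.8% |

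Two such subjects suffice for DMC referral. One would suffice if another subject met any of criteria 6, 9, 10, 11 or 12.

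**The case against.** The strongest reply is that a zero in the TEMA table is true for what the table claims to count, and that nothing obliges a reporting cut to equal a withdrawal trigger. The case also has other routes into the report. The AE definition in protocol section 9.1.1 includes abnormal laboratory findings, the eCRF records the primary reason for withdrawal, and the SAP plans disposition, AE-discontinuation and cytopenia outputs besides the by-visit minima and maxima. All of this stands, so the point is not that the case would vanish from the report. What remains is that none of these outputs counts subjects by grade and persistence, and that the AE-based ones depend on an AE being recorded.

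Three stronger readings are tempting and are not supported:

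- *Neutropenia that limits treatment has already been seen with the drug.* Protocol section 2.2.1 says of the psoriatic arthritis study: "There was a reduction in mean neutrophil count in the active treatment group, although this drop was not clinically relevant", and adds that "a clear relationship with dose or time was not evident". That is a change in a mean, with no graded neutropenia and no withdrawal reported.
- *The withdrawal rule keeps values from reaching Grade 3, so an empty table reflects the rule.* The documents give no rate of progression from Grade 2 to Grade 3. The reported half-life is about 28 days, laboratory tests continue at the withdrawal and SFU visits, and the all-visits category counts unscheduled values. Later progression could still be captured.
- *The primary objective would be answered too favourably.* The primary variable is the exposure-adjusted incidence of TEAEs, not TEMA.

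**Conclusion.** The mismatch is real but limited. Any number of subjects withdrawn for a Grade 2 value that stays at Grade 2 is compatible with a TEMA count of zero, and such subjects are also absent from the TEMA listing. Grade 2 alone does not have this effect; the value must be confirmed on both repeats.

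The logic rests only on the documents' rules. The sizes shown rest on assumed counts and risks, because the documents give no incidence of persistent Grade 2 values. The CTCAE Grade 2 limits for ANC are not in the documents and are not used here. I would class this as a cheap improvement to a secondary safety table. It is not a flaw in the primary analysis and not a contradiction in a clinical rule.

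**What to change.** In SAP section 11.3 and Table 14-2:

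1. For the variables already listed, add the number and percentage of subjects by worst CTCAE grade after the first PS0018 dose (Grade 2; Grade 3 and above). Use the CTCAE version already cited there, where it defines a Grade 2, and include unscheduled values as the all-visits TEMA category does.
2. Add a count, by parameter, of subjects at Grade 2 or above on the initial value and both repeats, shown separately from those with any value at Grade 3 or above. Derive it from the laboratory data, since the documents do not show that the withdrawal criterion number is captured.
3. Reconcile SAP section 14.3.4, where one sentence includes both serious and non-serious cytopenia events and the next confines the search to serious ones.

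The withdrawal and stopping rules are not touched.

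The cost is SAP wording, the Grade 2 limits to be entered, and a derivation linking a first Grade 2 value to its repeats. Criterion 10 already requires the retests, and protocol section 9.7 directs unscheduled tests to the central laboratory, so no new assessment is needed. The downside is a slightly longer table and laboratory results that look less favourable.
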